11.4.6 Deviation(s) from the original statistical plan

If substantial deviations of the analyses as outlined in these sections are needed for whatever reason, the protocol will be amended. All deviations of the analyses from the protocol or from the detailed statistical analysis plan will be listed and justified in a separate section of the final statistical report.

11.5 Handling of missing data and drop-outs

For the primary outcome, which is measured 5 min after aPDT, we do not expect any missing values since loss to follow-up is very unlikely. We plan to do complete case analyses of the primary and the secondary outcomes. Should more than 5 % of the primary outcome measurements be missing, we would use multiple imputation of the missing primary outcome data. The final number of imputations per missing value would be determined by the fraction of missing information (21).

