6. CLINICAL INVESTIGATION DESIGN

6.1 General clinical investigation design and justification of design

Design and rationale

This is a randomized controlled prospective study. Randomization of participants to either experimental or control group is necessary to reduce bias caused by concomitant treatment / medication and to investigate the additional effect of aPDT (activated photosensitizer) over the disinfection effect of chlorhexidine gluconate or unactuated methylene blue.

Intended procedures

Preoperative consultation:

After patient information and obtaining of informed consent, the inclusion and exclusion criteria are checked, and patient demographic data and medical history are obtained. Data will be taken from their medical records in the clinical information system (KIS).

Surgery day:

Random assignment of patients to experimental or control group.

Consent to participate will be updated after admission to the hospital on the day of surgery.

After Intubation and during positioning and final preparations for surgery, participants will then be administered the medical device as described under 8.1.1 Experimental Intervention (medical device) depending on assignment to experimental or control group (no light activation in control group).

Participants will be asked about their subjective evaluation of the treatment on the first postoperative day (Visit 2). For outpatient procedures, the survey is carried out by telephone.

Additional nasal swab for the subgroup after open reduction and internal fixation of midfacial fracture on day 2 (Visit 3; day of hospital discharge)

Visit day 14 (+/- 1)

Participants will be revisited 14 days (+/-1 d) after intervention (Visit 4) as part of the regular follow up consultation. The appointment will be made before discharge from the hospital. All participants will be interviewed about possible adverse effects and a third nasal swab test for microbiological analysis will be performed.

Limitations of the design

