7.4 Criteria for withdrawal / discontinuation of subjects

Withdrawal of subjects

If a clinically significant finding is identified after enrollment in the study (including, but not limited to changes from baseline), the principal investigator or qualified designee will determine if any change in participant management is necessary. Any new clinically significant finding will be reported as an adverse event (AE).

Participants are free to withdraw from participation in the study at any time upon request.

An investigator may exclude or withdraw a participant from the study for the following reasons:

- significant non-compliance with the study intervention due to intolerance of the nasal illumination
- if any clinical adverse event or other medical condition occurs such that continued participation in the study would not be in the best interest of the patient

The reason for the participant's discontinuation or withdrawal from the study will be recorded in the Case Report Form (CRF). Subjects who sign the informed consent form and are enrolled in the study, but do not receive the study intervention, may be replaced. Subjects who receive the study intervention and subsequently withdraw, or are withdrawn or discontinued from the study, will not be replaced.

Patients lost to follow-up

Participants are considered "lost to follow-up" if they fail to report for scheduled study visits and cannot be reached to complete all protocol-required study procedures.

The following actions will be taken if a participant fails to attend a required study visit:

- The investigator will attempt to contact the participant and reschedule the missed visit for 1 day. These contact attempts will be documented in the participant's study file.
- Should the participant continue to be unreachable, they will be considered to have withdrawn from the study with a primary reason of "lost to follow-up".

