8.4 Data collection and follow-up for withdrawn subjects

The reason for withdrawal will be noted in the CRF as described in chapter 7.4. In case of withdrawal, no further data will be collected. If the reason for the withdrawal is any problem related to the safety or performance of the medical device, the principal investigator will ask the subject for permission to follow their status and condition outside of the study. The data collected at the time of withdrawal will be used for statistical analysis in accordance with Art. 3 Abs. b ClinO-MD and subsequently anonymized. All biological material will be destroyed after evaluation.

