9.2.6 Patients lost to follow up

Participants are considered "lost to follow-up" if they fail to report for scheduled study visits and cannot be reached to complete all protocol-required study procedures.

The following actions will be taken if a participant fails to attend a required study visit:

- The investigator will attempt to contact the participant and reschedule the missed visit for the next day and will counsel the participant on the importance of maintaining the assigned appointment and inquires as to whether the participant wishes to and/or should continue participating in the study.
- Should the participant continue to be unreachable, they will be considered to have withdrawn from the study with a primary reason of "lost to follow-up".

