9.3 Procedures at each visit

9.3.1 Screening visit (Visit 0)

The screening visit takes place as part of the regular consultation hours for Oral- and Maxillofacial Surgery. Patients will be informed about the study. Informed consent will be obtained. Inclusion and exclusion criteria will be reviewed. Demographic information, patient's medical history and survey of concomitant treatments will be obtained.

9.3.2 Visit 1

The first visit will take place during preparation for surgical intervention. Patient is already under general anesthesia. Randomization takes place according to description 6.2.1.

Nasal swab + aPDT

Nasal swab test 3 minutes before the study intervention as described under 8.1.3. Administer study or control intervention as described under 8.1.1 and 8.1.2.

Nasal swab + follow up

After treatment, a second nasal swab test (5 minutes post intervention) for analysis of primary outcome will be taken.

In case of AE / SAE and/or device deficiencies the corresponding eCRF forms are recorded.

9.3.3 Visit 2

The second visit will take place on first postoperative day. The study investigator (not the same investigator who carried out the study intervention) will record the survey of concomitant treatment, survey of expected side effects and AE / SAE. In addition, scheduling of visit 3 on day 14 (+/- 1) post intervention is carried out. For outpatient procedures, visit 2 is carried out by telephone.

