9.3.4 Visit 3 (only subgroup following ORIF of midface fracture)

The third study visit is on the day of discharge from hospital (day 2) and contains an additional nasal swab test (pooled for both nostrils as described under 8.1.3).

9.3.5 Visit 4

Study Visit 4 will be held combined with the regular follow-up after surgery (wound control, removing sutures etc.). Recording of survey of concomitant treatment, expected side effects, AE/SAE will be recorded. A third nasal swab test is performed for microbiological analysis to assess secondary objective. Last step during visit 4 is documentation of study end eCRF form.

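### The longitudinal mixed model in 11.4.3 omits baseline score and surgery type, so its day-2 time term partly reflects surgery type; 11.5 and the lost-contact rules also need clearer wording

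*Combined protocol and SAP*

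**What the plan says.** **The mixed model.** Section 11.4.3 analyses the post-intervention scores at 5 minutes, day 2 (midface ORIF only) and day 14 as repeated measurements in one mixed-effects proportional odds model. It lists treatment and time, and adds their interaction in a further model. Neither baseline score nor surgery type appears. Section 11.4.2 gives adjustment for both as the aim of the primary regression, although its later list of explanatory variables names only surgery type and treatment. The separate day-14 and day-2 regressions are to be done similarly to the primary one. Section 4.3 names baseline in the longitudinal objective. Section 6.2.1 stratifies randomization by surgery type, and 9.2.2 restricts the day-2 swab to the ORIF group, about 100 of 208 patients in the synopsis.

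**Missing data.** Section 11.5: "We plan to do complete case analyses of the primary and the secondary outcomes". Multiple imputation is foreseen for the primary outcome only.

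**Lost contact.** After a missed required visit, 7.4 says: "The investigator will attempt to contact the participant and reschedule the missed visit for 1 day". Section 9.2.6 continues: "Should the participant continue to be unreachable, they will be considered to have withdrawn from the study", with lost to follow-up as the recorded reason. Section 8.4, repeated in 9.2.4, says: "In case of withdrawal, no further data will be collected". Section 9.3.3 says: "For outpatient procedures, visit 2 is carried out by telephone". On the day-14 appointment, 6.1 says "The appointment will be made before discharge from the hospital", while 9.3.3, describing the day-1 contact, says "In addition, scheduling of visit 3 on day 14 (+/- 1) post intervention is carried out". Section 9.3.5 says: "Study Visit 4 will be held combined with the regular follow-up after surgery".

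**The concern.** In the mixed model the 5-minute and day-14 means come from all patients and the day-2 mean from one randomization stratum. If ORIF patients differ in colonization level from the rest, a model without surgery type attributes part of that difference to time. Section 11.4.3 itself says that concomitant treatment depends on the operation and may influence colonization, so a difference is plausible. The model could then describe a day-2 rise or fall that is partly a contrast between types of surgery. Leaving out baseline costs precision, and it leaves the model without one of the time points that the longitudinal objective names.

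Two wording gaps bear on the same analyses. Section 11.5 does not say whether complete case refers to patients or to scores. And the lost-contact rule, read literally, could turn an unanswered day-1 call to an outpatient into a withdrawal that stops collection of the day-14 swab and survey.

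**Working it through.** **1. The plan's own figures.** With a difference of 3, SD 6, two-sided 5% and 90% power, a t-test needs 85 per arm, 170 in total (exact power at 170: 0.8999). 170/0.864 = 196.8, rounded up to an even 198. 198 × 1.05 = 207.9, so 208. (Dividing by 0.95 gives 208.4, so 209; this has no bearing here.) The stated 170, 198 and 208 are reproduced. SD 6, 208 and 198 are used below. Day 14 is not powered in the plan, so using SD 6 there is an assumption.

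**2. Day-2 time term without surgery type.** Linear analogue: random intercept, within-patient correlation ICC (assumed), 100 ORIF and 108 other patients, no true change over time, and an ORIF-versus-other difference of δ points that is the same in both arms.
- The ORIF mean lies δ × 108/208 = 0.519δ above the overall mean.
- Each ORIF patient also has 5-minute and day-14 scores. Through these the model recovers a share 2·ICC/(1 + ICC) of that excess.
- The remainder goes into the day-2 term: 0.519δ × [1 − 2·ICC/(1 + ICC)].

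| ICC | 1 − 2·ICC/(1 + ICC) | Day-2 leakage per point of δ |
|---|---|---|
| 0.3 | 0.538 | 0.28 |
| 0.5 | 0.333 | 0.17 |
| 0.7 | 0.176 | 0.09 |

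A generalized least-squares solution with 50 ORIF and 54 other patients per arm gives the same three values. With surgery type added, the leakage is zero. If the target of 50 in 6.2.1 meant 50 ORIF patients in total rather than per arm, 158/208 = 0.760 replaces 0.519 and the leakage is 0.41, 0.25 and 0.13.

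**3. Treatment terms.** In the same calculation with the treatment-by-time interaction included, leakage into the treatment effect, treatment-by-day-2 and treatment-by-day-14 is zero at all three correlations. The ORIF share is equal in both arms, so the surgery difference cancels.

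**4. Precision of the day-14 treatment contrast.** SE ≈ 6 × √(4/198) × √(1 − r²), with r the assumed correlation between baseline and day-14 score and 198 patients evaluable.
- Baseline not used: 6 × 0.1421 = 0.85.
- r = 0.3: 0.853 × 0.954 = 0.81; variance ratio 1/(1 − 0.09) = 1.10.
- r = 0.5: 0.853 × 0.866 = 0.74; variance ratio 1/(1 − 0.25) = 1.33.

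**5. What complete case would mean.** Day 2 is absent by design in 208 − 100 = 108 patients. Deleting every patient without all three scores would leave ORIF patients only. Using every observed score leaves all patients in the model.

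**6. Lost contact.** Sections 7.4 and 9.2.6 lead from a missed required visit, through continued failure to reach the patient, to withdrawn status. Sections 8.4 and 9.2.4 lead from withdrawal to no further data. No missed-visit status stands between them. For outpatients the day-1 visit is a telephone call, and under 9.3.3 it is also when day 14 is scheduled; under 6.1 that was done before discharge.

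**The case against.** The strongest reply is that no treatment comparison is distorted. Step 3 bears this out: only the day-2 main time term moves. Section 11.4.3 also plans a day-2 analysis within ORIF patients, where the confounding cannot arise, and a separate day-14 regression modelled on the primary one, so the precision loss belongs to the mixed model and not to the planned day-14 result. All of this stands.

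A reader might infer that 11.5 makes the mixed model impossible to fit. The documents do not support that. Analysing observed scores without imputation is an ordinary meaning of complete case and is compatible with the model, and 11.4.3 labels day 2 as ORIF-only, so an unscheduled swab need not count as missing. What remains is an undefined term.

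A reader might also infer that an unanswered day-1 call will remove outpatients from day-14 follow-up. The text permits that reading but does not compel it. The patient must remain unreachable, and one who attends routine follow-up may be taken as reached. Section 9.2.6 provides for asking whether the patient wishes to continue, and Table 1 allows unscheduled visits. For inpatients, scheduling on day 1 and scheduling before discharge can agree.

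Finally, section 11 defers detailed methods to a statistical analysis plan to be finalized before database closure. That is a suitable place for the correction, but the text available does not yet contain it.

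**Conclusion.** The point holds as a minor, cost-free improvement to the longitudinal model. Without surgery type, the day-2 main time term carries about 0.09 to 0.28 points per point of ORIF-versus-other difference on the 0–27 score. This rests on a linear analogue, about 100 ORIF patients and an ICC of 0.3 to 0.7; the documents give neither the difference nor the correlation. The absence of bias in the treatment terms assumes that the surgery difference is the same in both arms. On the odds-ratio scale there is a further reason to align the covariates: odds ratios are non-collapsible, so an unadjusted mixed-model estimate does not target the same quantity as an adjusted day-14 estimate. The precision gain from baseline (SE 0.85 to 0.81 or 0.74) depends on the assumed correlation.

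The primary outcome and its sample size are untouched. The points on 11.5 and on lost contact are matters of wording. The number of patients who might lose a day-14 swab is not documented, and no direction of bias is established.

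**What to change.** **In 11.4.3:** add baseline score and surgery type to both versions of the mixed model, report the day-14 treatment contrast from the treatment-by-time version, and restrict statements about day 2 to the ORIF stratum. Adding baseline as a covariate does not by itself give the change from baseline named in 4.3, so say where that comparison will be reported.

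**In 11.5:** state that for the mixed model complete case means that all observed scores are used, and that a day-2 swab not scheduled by design is not missing data.

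**In 7.4, 8.4, 9.2.4 and 9.2.6:** reconcile the wording so that a missed contact is recorded as such and does not by itself stop the day-14 swab and survey in a patient who attends. Reconcile 6.1 with 9.3.3 on when the day-14 appointment is made.

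**Cost:** protocol and SAP wording and a small change to the model code. The sample size stays at 208. No visit or measurement is added, since both covariates are already collected and day 14 is part of routine follow-up.

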12. QUALITY ASSURANCE AND CONTROL

The principal investigator implements and maintains quality assurance and quality control systems with written SOPs and work instructions to ensure that study conduct, data generation, documentation, and reporting follow the protocol, GCP, and applicable regulatory requirements. Monitoring and audits will be conducted during the investigation for quality assurance purposes.

12.1 Data handling and record keeping / archiving

The collection, transmission, storage, and evaluation of personal data within the scope of this project is carried out in accordance with the applicable Swiss data protection regulations. All investigation-related documents will be archived.

12.1.1 Case Report Forms

The investigators will use electronical case report forms (eCRF; REDCap, Vanderbilt University), one for each enrolled study participant, in which all relevant data of the participant are entered during the study (according to parameter table eCRF). All participants who were either enrolled in the study or deemed ineligible or were eligible but not enrolled in the study will additionally be documented in a screening log. The investigator will document the participation of each patient on the enrollment log.

All clinical data will be stored in medical history of the patient in KISIM. For study specific data collection and storage eCRF will be used. In case of premature discontinuation or withdrawal the reason will be documented in the eCRF.

All data are protected on a secure clinical network only allowing access for study staff according to staff list. It is the responsibility of the principal investigator to ensure that all data are entered completely and correctly in the respective database during the investigation. Corrections in the eCRF may only be done by the principal investigator or by other authorized persons. In case of corrections, the original data entries will be archived and can be made visible if needed. For all data entries and corrections, the date, time of day, and person making the entries will be logged automatically by the eCRF.

The eCRFs must be kept up to date to reflect participant status at each phase of the study process. Participants must not be identified by name in the eCRF. Appropriate coded identification (participant number and year of birth) will be used.

Care will be taken to identify each authorized investigator who may make data entries and changes in the CRF. A list of signatures and initials of all authorized individuals will be placed in the study site file and the trial master file, respectively.

Documented medical histories and reports of participant progress during the study will be maintained. These records will include originals or copies of laboratory and other medical test results (microbiology test results) to be maintained in each participant's eCRF.

The investigators assure to make a complete and accurate documentation of the participant data in the eCRF. All data entered in the eCRF will also be available in the individual participant file.

12.1.2 Specification of source data and source documents

The following documents are considered source data, including but not limited to:

- SAE worksheets
- Nursing staff records, records of clinical coordinators

Source data are available at the site to document the existence of the study participants and demonstrate the integrity of the study data collected. Source data includes the original documents relating to the study, as well as the participant's medical treatment and medical history.

The following information will be included in the source documents:

- Demographic data (age, gender)
- Inclusion and exclusion criteria details
- Participation in the study and signed and dated Informed Consent Forms (ICF)
- Visit dates
- Key efficacy and safety data (as specified in the protocol)
- SAEs (related) and concomitant medication
- Results of the microbiological analysis

12.1.3 Archiving of essential clinical investigation documents

All documents of this investigation will be archived for a minimum of 10 years after a regular or premature termination of the investigation in accordance with Art. 40 ClinO-MD. All data will be stored securely at the department of oral and maxillofacial surgery, University Hospital Zurich. The principal investigator is responsible for the secure storage of all documents.

12.2 Data management

Only authorized personnel will have access to the data. Data will be entered from the source documents into the eCRF on the day of participant registration. After statistical analysis, data will be anonymized by destroying the key (the document linking identifiable data to the pseudonymized participant number).

12.2.1 Data management system

For data and query management, monitoring and reporting a digital data acquisition will be done (eCRF, REDCap). It is the responsibility of the principal investigator to ensure that all data are entered completely and correctly in the respective database during the investigation. Appropriate training will be provided by the Clinical Trials Center.

12.2.2 Data security, access, and back-up

Only authorized personnel will have access to the data, this includes the investigators and designated members in case of monitoring or audits.

12.2.3 Analysis and archiving

Data entry will be done by authorized personnel at the site. Data from the laboratory-results will be available and collected over the clinical information system, anamnestic data collected by authorized personnel and patient questionnaires' will be transferred to the eCRFs. After the data collection period, the data will be transferred to local storage provided by the investigator. The collected data will be stored for 10 years after completion of the trial at the investigator's facility.

12.2.4 Electronic and central data validation

All Data will be stored in the Study Files. Access will be limited to personal involved in collection, analysis, maintenance or safety monitoring and hospital personal involved in treatment of the study patients. Where data is stored or transferred electronically it will be done according to Swiss data protection laws. Completion checks and validation of the data in the eCRFs will be done by personal authorized from the investigator periodically.

